1 SYNOPSIS

Study title

Radiesse® Post Approval Safety Study for the Treatment of Hands With Moderate to Very Severe Dorsal Volume Loss

Study phase

Device Post-Market

Study Product

Radiesse Injectable Implant

Indication

Hand augmentation to correct volume loss in the dorsum of the hand

Study objectives

The primary objective of this study is to evaluate the safety of Radiesse implantation for very severe volume loss in the dorsum of the hands at 6 months after treatment. The primary endpoint is a non-inferiority hypothesis test to demonstrate that the proportion of subjects with device/injection-related severe adverse events (AEs) in hands that were grade 4 at baseline as determined by the Merz Hand Grading Scale¹ (MHGS, **Figure 1**) is not significantly worse than the combined proportion of subjects with device/injection-related severe AEs in hands that were MHGS grades 2 or 3 at baseline.

A secondary objective of this study is to evaluate the effectiveness of Radiesse implantation for very severe volume loss in the dorsum of the hands. The effectiveness endpoints will be measured by assessing ≥ 1 point improvement from baseline in both hands of MHGS grade 4 subjects at 3- and 6-months after initial treatment.

Another secondary objective of this study is to evaluate the safety of multiple retreatments with Radiesse in the dorsum of the hands. The hypothesis is that multiple retreatments with Radiesse do not introduce new concerns of safety.

Hand function testing will also be performed by 2 test administrators at each site to evaluate the effect of Radiesse injection on hand function.

SOP/245/EN - CLINICAL STUDY PROTOCOL Page 6 of 48 Merz North America, Inc. Confidential and Proprietary Information. Do not disclose without authorization.

¹ Carruthers, et al., "A Validated Hand Grading Scale," Dermatol Surg 2008, 34:S179-S183.

Study population, diagnosis, and main criteria for in- and exclusion

A maximum of 250 subjects at least 22 years of age with moderate to very severe volume loss in the dorsum of their hands will be enrolled based on the MHGS (**Figure 1**), approximately 125 with moderate to severe volume loss (MHGS grades 2 and 3) and approximately 125 with very severe volume loss (MHGS grade 4). Exclusion criteria include participation in the pre-market Radiesse hand treatment study (Merz #P110607), previous fat injections, hand deformities, or surgery in the dorsum of the hands, and any medical condition with the potential to interfere with the study or increase the risk of AEs. See Section 7 for the full list of in- and exclusion criteria.

Study design

This is a prospective 2-year post approval study (PAS) evaluating the AE rate of MHGS baseline grade 4 hands (Group A) compared to the AE rate of MHGS baseline grade 2-3 hands (Group B). Subjects will be recruited at each site with the intention to have an equal number of subjects in Group A and Group B. All subjects will receive an initial Radiesse hand treatment in both hands, and up to 3 retreatments in the study. Hands will be assessed by evaluators on the MHGS who will be blinded to group, treatment details, time since last treatment, and number of retreatments. Subjects will assess satisfaction with treatment results on the Global Aesthetic Improvement Scale (GAIS, **Table 1**).

AE assessments

will be made by the treating investigator at all study visits, and subjects will complete a 30-day take-home diary after each treatment received in the study to self-report AEs. Hand function testing will also be performed by 2 test administrators at each site to evaluate the effect of Radiesse injection on hand function.

Duration of treatment per subject

Subjects will be in the study for approximately 24 months. Subjects will be treated with Radiesse in the dorsum of the hands at enrollment and will have the opportunity to receive up to 3 repeat treatments over 2 years of follow-up. The retreatment interval is every 6 months as agreed upon by the treating investigator and the subject.

Total number of subjects and number of countries

There will be a maximum of 250 subjects enrolled and treated in the United States.

Number of study sites

This study will be conducted at up to 12 study sites.

3 ETHICS

3.1 Institutional Review Board

The following documents must be submitted to the responsible Institutional Review Board (IRB): this protocol, the Informed Consent Form (ICF), relevant supporting information, and all types of subject recruitment or advertisement information. These documents must be approved by the appropriate IRB before the study is initiated. Any amendments to the protocol must also be approved, where necessary, by the IRB prior to implementing changes in the study. Documentation of these approvals must be provided to the Sponsor prior to the initiation of the amendment. The IRB used must comply with current Good Clinical Practice (GCP) and guidelines.

The investigator's responsibilities (at a minimum) regarding the IRB are as follows:

- Obtain IRB approval of the protocol, informed consent, and any advertisements to recruit subjects prior to their use.
- Obtain IRB approval for any protocol amendments and ICF revisions before implementing the changes.
- Provide the IRB with any required information before and during the study.
- Submit progress reports to the IRB, as required, during the conduct of the study; request re-review and approval of the study, as needed; provide copies of all IRB re-approvals and relevant communication to the Sponsor.
- Notify the IRB within 10 days of all serious and unexpected AEs related to the study device that are reported to the investigator by the Sponsor. The investigator is responsible for updating the IRB on the progress of the study and of any changes made to the protocol as deemed appropriate, but (in any case) at least once a year. The investigator must also keep the IRB informed of any AEs of interest, according to the IRB policy.

3.2 Ethical conduct of the study

This study will be conducted in accordance with all applicable local and federal regulations. Regulatory authorities will be notified and consulted, as required, prior to, during, and after the conduct of the study.

This clinical trial will be conducted in compliance with the protocol, International Conference on Harmonisation (ICH), GCP guidelines, and other applicable regulatory requirements.

3.3 Informed consent

The investigator is responsible for obtaining written informed consent from each individual participating in this study after adequate explanation in layman's terms regarding the nature of the study, along with the aims, methods, objectives, and any

SOP/245/EN - CLINICAL STUDY PROTOCOL Page 9 of 48 Merz North America, Inc. Confidential and Proprietary Information. Do not disclose without authorization.

potential risks. The ICF must be appropriately signed and dated by the subject or the subject's legally authorized representative and the person obtaining the consent (if required by the IRB) prior to conducting/obtaining any study-related assessments, including the discontinuation of any medications prohibited for the study. The subject will be given a copy of the signed and dated written ICF as well as all ICF updates (if applicable).

If the ICF is amended during the study, the investigator must follow all applicable regulatory requirements pertaining to approval of the amended ICF by the IRB and use of the amended form (including for ongoing subjects).

During the course of the study, the subject will be informed in a timely manner if information becomes available that may be relevant to the subject's willingness to continue participation in the study. In case of AEs, the subject should inform the investigator, who then will make a judgment whether continuing in the study serves the subject's best interests. The subject, however, is free to withdraw consent at any time and for any reason, whether expressed or not.

Each ICF will contain contact information with a phone number the subject should contact if they have medical concerns 24 hours a day.

The original and any amended signed and dated ICF must be retained at the study site; and a copy must be given to the subject or subject's legally authorized representative(s).

4 INTRODUCTION

4.1 Study background

The clinical study is a PAS being conducted to satisfy a condition of the June 4, 2015, PMA-S (P050052/S049) approval of Radiesse injectable implant indicated for hand augmentation to correct volume loss in the dorsum of the hand, to provide safety and effectiveness data in subjects with more severe volume loss (MHGS grade 4) than those subjects evaluated in the pre-market study. The pre-market (Merz protocol #P110607) study cohort excluded subjects with baseline grade 4 hands. This study will also provide additional data specific to safety of multiple retreatments.

4.2 Study rationale

Radiesse dermal filler was demonstrated to be safe and effective in the pre-market study for treatment of hands with moderate to severe dorsal volume loss. On the validated MHGS (**Figure 1**), these were hands rated as grade 2 or grade 3 at baseline, or before treatment. On the MHGS, these hands had moderate to severe dorsal volume loss. Subjects with MHGS grade 4 (MHGS4) hands at baseline, or very severe dorsal volume loss, were excluded from the pre-market study. With the Food and Drug Administration (FDA) approval of Radiesse for treatment of the hands, it is anticipated that patients that present with MHGS4 hands will seek treatment. This PAS will evaluate the safety and effectiveness of Radiesse treatment in MHGS4 hands with very severe dorsal volume loss. Subjects will receive an initial Radiesse hand treatment and have the opportunity to receive up to 3 repeat treatments over 2 years of follow-up.

A non-inferiority hypothesis test will be conducted for the primary study endpoint. The hypothesis test will compare the 6-month rate of device/injection-related severe AEs in the MHGS4 subjects (Group A) versus a subjects with baseline MHGS grade 2 or grade 3 (MHGS2-3, Group B).

4.3 Risk-benefit assessment

Potential risks associated with the injection of Radiesse into the dorsum of the hand to restore volume loss are similar to injections performed with any other commercially available cosmetic dermal filler, such as bruising, swelling and redness. For complete safety and risk information, see the Instructions For Use (IFU, **Appendix A**). Lidocaine is approved as a local and regional anesthetic and will be mixed in-office with Radiesse. Potential side effects associated with lidocaine are a risk of participating in this study and include lightheadedness, nervousness, apprehension, euphoria, confusion, dizziness, drowsiness, ringing noise in the ears, blurred or double vision, vomiting, sensations of heat, cold or numbness, twitching, tremors, convulsions, unconsciousness, respiratory depression and arrest, slow heartbeat, hypotension, and cardiovascular collapse, which may lead to cardiac arrest. However, these side effects are unlikely to occur at the low

doses of lidocaine being used in this investigation. Lidocaine is beneficial in terms of pain reduction during and after the study procedure.

A potential benefit of participating in this study is to have correction of volume loss and reduction of the prominence of veins and tendons in the dorsum of one or both hands. Additional potential benefits of improving the appearance of the hands could include enhanced emotional well-being with improved satisfaction with the appearance of the hands, or the perception of having a more youthful appearance.

5 STUDY OBJECTIVES AND ENDPOINTS

5.1 Objectives

The primary objective of this study is to evaluate the safety of Radiesse implantation for very severe volume loss in the dorsum of the hands.

Secondary objectives of this study include evaluation of the effectiveness of Radiesse implantation for very severe volume loss in the dorsum of the hands, the safety of multiple retreatments with Radiesse in the dorsum of the hands, and to support the hypothesis that multiple retreatments with Radiesse do not introduce new concerns of safety.

Hand function testing will also be performed by test administrators at each site to evaluate the effect of Radiesse injection on hand function.

5.2 Endpoints

The primary safety endpoint of the study is the 6-month rate of device/injection-related severe adverse events

The secondary endpoints of the study are:

- The rate of device/injection-related severe adverse events at 24 months
- MHGS at 3-months after initial treatment
- MHGS at 3-months following retreatment for those receiving retreatment
- GAIS at 3-months after initial treatment
- GAIS at 3-months following retreatment for those receiving retreatment
- Hand function testing at baseline, study exit, and other collected time points
 - Inter-rater correlation of hand function testing results for each site
 - Differences between sites in hand function testing results

Figure 1. Merz Hand Grading Scale (MHGS).

6 INVESTIGATIONAL PLAN

6.1 Overall study design

This is a prospective, open-label 2 year post approval study in up to 250 subjects to evaluate the safety and effectiveness of Radiesse implantation for very severe volume loss in the dorsum of the hands in MHGS4 subjects. The primary objective of evaluating the safety of treatment of MHGS4 subjects will be comparing the 6-month rate of device/injection-related severe AEs in the MHGS4 group (Group A) versus the MHGS2-3 group (Group B). All subjects will be new subjects who did not participate in the pre-market Radiesse hand treatment study (Merz #P110607). Subjects will be consented at up to 12 investigational sites in the United States.

Multiple assessments will be performed at study visits. Some of the main assessments include:

- Hand function testing to be performed by two site hand function testers for first 10 subjects enrolled at each site, and by one hand function tester for all other subjects enrolled at each site - to evaluate measurable functional effect(s) of Radiesse injection on hand function. A minimum of 50 subjects across all sites will be evaluated by two independent hand function testers.
- MHGS (Figure 1)- a single blinded site evaluator will grade the hands using the MHGS
- Photographs at baseline and exit from the study, and during the study to document a serious or medically concerning adverse event in the hands. At the 2-week follow-up visit, hand photographs will also be taken in subjects who have a device and/or injection-related severe adverse event.
- GAIS (Table 1) subjects will rate the aesthetically pleasing aspect of the Radiesse hand treatment using the GAIS
- AE Subject Diary subjects use this to collect any AEs for 30 days post injection

6.1.1 Study visits

Subjects will be required to present for 8 to 11 in-office visits and receive 1 to 4 followup phone calls during their 24-month study participation. If a subject only receives the initial treatment at enrollment, there will be a total of 8 visits and 1 follow-up phone call. For each of the 3 optional repeat treatments received, there will be an additional followup phone call (72-hours post injection) and a visit scheduled 1-month after each repeat treatment. The Visits will include a Screening/Enrollment/Baseline Visit in which the subject receives their first injections of Radiesse. After Enrollment, there will be a 72-hour follow-up phone call made to each subject to assess AEs and/or any changes in concomitant medications. Subjects will be seen at the study site for follow up visits at Months 1, 3, 6, 12, 18, and 24. If they are administered repeat injections at any of the Months 6, 12 and 18 visits, they will receive a 72-hour follow-up phone call following each injection and return for follow up visits 1 month post-injection at Months 7, 13, and/or 19 respectively.

6.1.2 End of study

The end of study will be defined as completion of all study visits by all enrolled subjects during the 24-month participation period. If an unforeseen device-related serious adverse event (SAE) or unanticipated serious device effect (USADE) occurs, the end of the study will be prolonged until clinical resolution of the event, or considered permanent as determined by the treating investigator.

The study or parts of the study may be discontinued by Merz North America, Inc. (Merz) or at the recommendation of an investigator after consultation with Merz at any time. This may be based on a significant number of AEs of a similar nature that warrant such action or at the request of Merz.

6.1.3 Study flow chart

Figure 2. Study design showing Radiesse treatment and follow-up visit schedule. In parentheses over the timeline are the follow-up visits that will be scheduled only if a repeat treatment is received at the 6-, 12-, or 18-month visit.

6.1.4 Study timeline

Milestone	Relative to date of FDA Approval				
Expected date of study initiation (First subject enrolled)	4 months				
Expected monthly number of study sites with IRB approvals	4				
Expected number of subjects enrolled per month	90				
Expected date for completion of subject enrollment (Last subject,	7 months				
first visit)					
Six Month Post-Approval Report to FDA	6 months				
One Year Post-Approval Report to FDA	12 months				
Eighteen Month Post-Approval Report to FDA	18 months				
Two Year Post-Approval Report to FDA	24 months				
Expected date for completion of study follow-up (Last subject last	31 months				
Expected date for submission of final report	34 months				

7.1 Selection of study population

Presenting subjects will be screened to the selection criteria identified in sections 7.2 and 7.3 below. The investigational site will recruit candidates and perform the screening, which could include use of patient databases, phone calls, email or postal mail distribution, and advertisements.

7.2 Inclusion criteria

Only subjects meeting all of the following inclusion criteria will be considered for study enrollment:

- 1. Has hands rating 2, 3, or 4 on the validated MHGS as determined by a live, masked evaluator.
 - Left and right hand with a rating of 4 of the validated MHGS will be assigned to Group A.
 - Left and right hands with a rating of 2 or 3 on the validated MHGS will be assigned to Group B.
- 2. Has left and right hands with a rating of 2 or 3 on the validated MHGS as determined by a live, masked evaluator if screened for Group B.
- 3. Is at least 22 years of age.²
- 4. Has signed an ICF.

² Pediatric populations or subpopulations generally do not suffer from the hand condition the device is intended to treat in the study protocol.

- 5. Understands and accepts the obligation not to receive any other procedures in the dorsum of the hands through the end of the study.
- 6. Understands and accepts the obligation and is logistically able to present for all scheduled follow-up visits and meet all study requirements.

7.3 Exclusion criteria

Subjects having any of the following criteria, either at screening or at baseline, will not be included in the study:

- 1. Was a participant in the Radiesse hands pre-market clinical study (Merz #P110607).
- 2. Has been treated with fat injections or Radiesse in the hands, has hand deformities, or has received surgery in the dorsum of the hands.
- 3. Has received within the past 6 months or plans to receive during the study dermal resurfacing procedures (e.g. chemical peel, dermabrasion, ablative laser resurfacing) or non-invasive skin-tightening (e.g. Thermage, Ulthera) in the dorsum of the hands during the study.
- 4. Has received in the past 2 weeks or plans to receive during the study, prescription wrinkle therapies, topical steroids, skin irritating topical preparations, or pigmenting agents (self-tanning agents) in the dorsum of the hands during the study.
- 5. Has received in the past 2 months, or plans to receive immunosuppressive medications or systemic steroids (intranasal / inhaled steroids acceptable) during the study.
- 6. Has an acute inflammatory process or infection, or history of chronic or recurrent infection or inflammation with the potential to interfere with the study results or increase the risk of AEs.
- 7. Has a known bleeding disorder or is receiving medication that will likely increase the risk of bleeding as the result of injection.
- 8. Has a known history of allergic / anaphylactic reactions, including hypersensitivity to lidocaine or anesthetics of the amide type, or any of the device components.
- 9. Has a known history of hyper- or hypo-pigmentation, keloid formation, or hypertrophic scarring.
- 10. Is a female of child bearing potential³ and not using medically effective⁴ birth control or is pregnant or lactating.

³ Childbearing potential is defined as NOT premenarche, permanently sterilized or postmenopausal (i.e., 12 months with no menses without an alternative medical cause).

- 11. Has any other medical condition with the potential to interfere with the study or increase the risk of AEs, such as: autoimmune disease affecting the hand, hand implants, Dupuytren's contracture, history of hand tumor, vascular malformations, Raynaud's disease, and patients at risk for tendon rupture.
- 12. Is enrolled or plans to enroll in an interfering study.
- 13. Is an employee or direct relative of an employee of the investigational site or of the study Sponsor.

7.4 Removal of subjects from treatment or assessment

7.4.1 Discontinuation of subjects

The subject may discontinue from the study at any time without any penalty or loss of benefits to which the subject is otherwise entitled. Date and discontinuation circumstances should be recorded.

Subjects must be discontinued from the study by the investigator at any time for any of the following reasons:

- Withdrawal of informed consent.
- Pregnancy.
- Any AE for which treatment continuation would constitute an unacceptably high risk for the subject.

Before discontinuation, every effort should be made to ensure that the subject returns for a final study visit. In the case of loss to follow-up subjects, every effort should be made to contact subjects lost to follow-up, and all such efforts should be documented in the subject file.

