12.1 Determination of sample size

The primary endpoint will be based on a non-inferiority hypothesis test comparing the 6month rate of device/injection-related severe AEs in the MHGS4 (Group A) subjects versus the MHGS2-3 (Group B) subjects. Based on the pre-market study data, an expected rate of severe adverse events is 17% for both groups, and the test will be based on a 12% non-inferiority margin. This margin allows for adequate power of the planned hypothesis test with a reasonable sample size and will provide assurance that the severe AE rate in the MHGS4 subjects is not unacceptably higher given the expected benefit in these subjects. The test will be based on a one-sided Farrington-Manning likelihood score test of binomial proportions at a one-sided 0.05 alpha level. A maximum of 250 subjects with MHGS grades 2, 3 and 4 at baseline (at least 50% with both hands rated MHGS 4) will be enrolled in at least 5 sites and a maximum of 12 sites in the US. Allowing for some attrition, a total of 244 subjects (122 in each group) at 6 months will provide approximately 80% power to conduct the hypothesis test. Based on an expected attrition rate of 5% per year, a minimum of 225 evaluable subjects are required to provide 2-year follow-up data. Safety and effectiveness data that are collected after 6 months and up to 2 years will be presented descriptively.

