7.1. Primary Safety Endpoint

The primary safety endpoint analysis will be based on a non-inferiority hypothesis test. Stated in terms of the null and alternate hypothesis, this is as follows:

Ho (null):  $P_A - P_B \ge 12\%$  vs

Ha (alternate): PA – PB < 12%

Where PA and PB are the percentages of subjects in Groups A and B who experience a device/injection-related severe adverse event by 6 months. Percentages will be calculated using the number of subjects experiencing at least one device/injection related severe treatment emergent adverse event (TEAE) by six months posttreatment as the numerator divided by the number of subjects in the SES (PPS) population with six month follow-up data.

TEAEs are defined as adverse events with onset or worsening after the first injection of Radiesse.

The test will be based on the Farrington-Manning likelihood score test. Testing will be done by constructing a one-sided 95% confidence interval using the Farrington-Manning method. If the upper 95% confidence bound around  $P_A - P_B$  is less than 12%, Ho will be rejected in favor of Ha, thus demonstrating non-inferiority, otherwise the Ho will be accepted.

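### The SAP does not say how to count a subject who has the primary event and leaves before Month 6; the two possible readings bias the primary rate in opposite directions

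*Protocol*

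**What the plan says.** Protocol 7.4.1 makes exit mandatory and places it at study level: "Subjects must be discontinued from the study by the investigator at any time for any of the following reasons". The listed reasons include "Any AE for which treatment continuation would constitute an unacceptably high risk for the subject". The section gives no route for stopping injections while remaining in follow-up, although it asks for every effort to obtain a final visit.

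Other parts of the protocol assume such a route exists. Section 6.1.1 gives a full visit schedule for a subject who has only the first treatment. The footnotes to Table 2 leave retreatment to the treating physician and the subject. Section 7 promises every effort to have all enrolled subjects complete.

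Protocol 12.2.1 bases the primary safety analysis on the Safety Evaluation Set (SES), meaning everyone exposed at enrollment. SAP 7.1 takes as numerator the subjects with at least one device/injection-related severe treatment-emergent event by six months, "divided by the number of subjects in the SES (PPS) population with six month follow-up data". The follow-up condition is attached to the denominator only, and six-month follow-up data is not defined. SAP 7.12 uses observed data only for this endpoint. SAP 7.2 has the same construction at 24 months. SAP section 8, which lists changes from the protocol, does not mention the narrower denominator.

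**The concern.** The primary endpoint is a safety event, and the exit rule is triggered by safety events. A subject can therefore have the primary event, be required to leave, and lack Month 6 data because of it. The SAP does not say whether that subject counts. An analyst could follow the wording, so that the numerator is no longer a subset of the denominator. Equally, an analyst could restrict both, because the Farrington-Manning test expects a binomial count out of a fixed set. The second choice removes subjects on the basis of the outcome.

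At stake are the size of the one formal test in the study and the interpretability of the two reported rates. Duration, resolution and recurrence data are also lost for any subject who leaves.

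**Working it through.** **Inputs from the documents.** Protocol 12.1 specifies a "one-sided Farrington-Manning likelihood score test of binomial proportions at a one-sided 0.05 alpha level". It also states that "an expected rate of severe adverse events is 17% for both groups", that "the test will be based on a 12% non-inferiority margin", and that "a total of 244 subjects (122 in each group) at 6 months will provide approximately 80% power". Enrollment is capped at 250, about 125 per group, and expected attrition is 5% per year.

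**The plan's own figure.** The unpooled formula n = (1.645 + 0.842)² × 2 × 0.17 × 0.83 / 0.12² gives 122 per group. Exact enumeration of the Farrington-Manning test at 122 per group gives 79.7% power at 17% vs 17% and 5.0% type I error at 29% vs 17%. The stated sample size reproduces and is not in dispute. Attrition also fits: 250 × 0.95^0.5 = 243.7 at six months.

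**One group, to show the direction.** Suppose 36 of 125 subjects have the event and 5 of those leave before Month 6.
- All exposed subjects: 36/125 = 28.8%.
- Literal SAP 7.1: 36/120 = 30.0%.
- Dropped from both: 31/120 = 25.8%.

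**Effect on the test.** Let p be the true rate and f the share of event subjects who leave before Month 6. All event-free subjects are taken as followed.
- Dropped from both: observed rate = p(1 − f) / (1 − pf).
- Literal: observed rate = p / (1 − pf).

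The true rates are set at the margin, 29% vs 17%, a difference of 12 points. The share f is an assumption, since the documents give none.

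| f, both groups | Reading | Group A | Group B | Apparent difference | Type I error |
|---|---|---|---|---|---|
| 10% | dropped from both | 0.261/0.971 = 26.9% | 0.153/0.983 = 15.6% | 11.3 points | about 6.5% |
| 20% | dropped from both | 0.232/0.942 = 24.6% | 0.136/0.966 = 14.1% | 10.6 points | about 8.8% |
| 10% | literal | 0.290/0.971 = 29.9% | 0.170/0.983 = 17.3% | 12.6 points | about 4.5% |
| 20% | literal | 0.290/0.942 = 30.8% | 0.170/0.966 = 17.6% | 13.2 points | about 4.1% |

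The first two error rates come from exact enumeration at the expected group sizes, and the last two from simulation with random exits. Starting from 122 or 125 per group, or fixing rather than drawing the exits within the first two rows, moves them by about 0.1 to 0.2 points.

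Unequal exits widen the gap. With 20% in Group A and 10% in Group B the error is about 14.0% (dropped from both) or 3.5% (literal). With 30% and 10% it is about 26.9% or 2.7%.

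**How plausible are these shares?** At 125 per group and 29% vs 17%, there are 36.25 + 21.25 = 57.5 expected event subjects. Planned attrition is 250 − 243.7, about 6 subjects from all causes by six months. An f of 10% needs about 5.8 event subjects to leave, which uses up nearly all of that. An f of 20% needs 11.5. The 30%/10% case needs 10.9 + 2.1 = 13.0.

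**With event subjects kept in both.** At 125 per group, exact type I error is 5.1% and exact power 80.7% when all event-free subjects are followed. If 2.5% of event-free subjects lack six-month data and are left out, the rates become 0.29/(0.29 + 0.71 × 0.975) = 29.5% and 0.17/(0.17 + 0.83 × 0.975) = 17.4%. The difference is 12.2 points, a small error in the conservative direction.

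**The case against.** A reader might infer that the exit rule biases the trial toward non-inferiority, because the subjects with the worst events disappear. The documents do not support that as a conclusion. The SAP puts the follow-up condition on the denominator only; taken at its word, early exit raises the rate and makes the test conservative.

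A reader might also infer that the primary event itself is lost. It is not. If the event that triggers exit is severe and related, it has already been recorded, and the endpoint needs only one. Nor is the trigger defined by severity or relatedness, so overlap with the primary event is likely but not stated.

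Timing limits the effect further. The trigger concerns continuing treatment, no injection is scheduled between enrollment and Month 6, and Month 6 retreatment follows data collection. The rule applies at any time, but it should act mainly after the primary window. Exit shares of 20% or more also go well beyond planned attrition.

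Protocol 6.1.2 is not a contradiction. It says that "the end of the study will be prolonged until clinical resolution of the event" or until the event is judged permanent, which concerns the end of the study after an unforeseen serious device event. That is a partial mitigation, and it does not reach a severe event that is not serious. The final visit in 7.4.1 and the full-SES proportion with Kaplan-Meier analysis in SAP 7.4 also help, but SAP 7.4 covers the whole study and supplies no six-month comparison on all exposed subjects.

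Finally, protocol 12.1 plans for 244 subjects at six months, which suggests that some loss from the analysis was foreseen. That explains the denominator, but it does not say how a subject with an event who leaves early is counted.

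All of this stands. It removes the claim of a known direction and leaves the undefined counting rule.

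**Conclusion.** The point holds as a gap in the SAP. The primary proportion is undefined for a subject with the event who leaves before Month 6. One reading gives a ratio that is not a binomial proportion; the other gives a proportion in a set selected by outcome. Both differ from the all-exposed analysis of protocol 12.2.1, and SAP section 8 does not record the departure.

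With an assumed 10% to 20% of event subjects leaving early in both groups, the nominal 5% test has a true size of about 6.5% to 8.8% or of about 4.5% to 4.1%, depending on the reading. Planned attrition makes the lower end the more realistic. If no event subject leaves before Month 6, there is no effect.

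The same gap matters more for the 24-month rate in SAP 7.2, because exits prompted by adverse events are likelier once retreatment begins. That endpoint is descriptive, so a misleading rate is at stake there rather than a test error.

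**What to change.** **SAP 7.1.** Count every SES subject with a qualifying event by six months in both numerator and denominator. Require six-month follow-up only of event-free subjects, and define what counts as such follow-up, including whether an early final visit qualifies. Add one sensitivity analysis of the six-month comparison, either on the full SES or by Kaplan-Meier estimates at six months, to cover event-free subjects who leave early.

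**SAP 7.2.** Apply the same counting rule at 24 months.

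**SAP section 8.** Record how the primary denominator differs from protocol 12.2.1.

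**SAP 7.6.** Show early exits by group and by whether a qualifying event had occurred, so that the exit share is known.

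**Protocol.** The sponsor should reconcile 7.4.1, which requires study exit for certain adverse events, with 6.1.1 and Table 2, under which subjects without retreatment stay in follow-up, and with section 7, which asks that all subjects complete. How that is resolved is for the sponsor to decide. SAP version 2.0 already refers to data collection in the past tense, so this may come too late to change visits; the SAP changes do not depend on it.

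The cost is slightly longer SAP text and one extra sensitivity analysis. No further subjects are needed.
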